## Randomization

Twelve selected schools will be randomly allocated into the intervention group and control group (intervention/control = 1:1) by having sealed opaque envelops drawn by the research staff. Six intervention schools will receive the peer-led theory-based intervention programs during a 6-month period. Six control schools will continue their present practice and receive oral health pamphlets only, such as oral health education class (if any).

### Introduction of the peer-led theory-based intervention

## a. Peer leader: selection and training

We plan to select 2-8 peer leaders in S2 students within each school in the intervention group. A total of 25-48 peer leaders will be selected and trained in this study. Students who meet these criteria will be considered as a priority: 1) demonstrate strong leadership, 2) have a willingness to participate in the training, 3) have prior experience to be a peer leader

An experienced behavioural scientist will train the peer leaders through lectures, workshops, and individual counselling. A variety of topics will be covered by the training, including

- 1) knowledge and skills related to oral health,
- adolescent's development and characteristics (e.g., Erikson's Psychosocial Development Theory),
- 3) introduction of SCT and HBM,
- 4) knowledge and skills related to peer leading,
- 5) how to conduct peer-led programs, and
- how to improve illness representations towards existing oral diseases (guided by Common-Sense Model of illness representations [37, 38]).

A total of 6 hours training (3 hours per day x 2 days) will be conducted during weekends. Peer leaders will practice in groups, and only those who pass the evaluation are allowed to conduct peer-led interventions. We will record the performance and give specific feedback to each peer leader.

## b. Contents of the intervention activities

A total of five peer-led activities will be conducted in the intervention schools by the well-trained peer leaders within a 6-month intervention period.

- In the 1st month of intervention, peer leaders will deliver a poster and a leaflet providing information on healthy oral behaviors based on SCT and HBM. Such materials will be provided at the entrance of the school gate, the canteen, and each class. Peer leaders will encourage students to ask questions when they receive such materials. Participants are free to take an on-site quiz to check assess their knowledge level,
- 2) In the 2nd month of intervention, peer leaders will give a specific health talk aiming to raise the awareness of healthy oral behaviors. Schools teachers will encourage all students to participate in this talk. We will video-record this health talk and make it available online to reach more students. This talk will be guided by SCT and HBM, and it will include short testimonials of the good experiences of the peer leaders when performing healthy oral behaviors,
- 3) In the 3rd month of intervention, peer leaders will organize a workshop aiming to help the participants practicing skills in performing healthy oral behaviors. Regarding different oral behaviors (tooth brushing, dental flossing, and dental visits), targeted skills will be practiced, and

- 4) In the 4th month of intervention, peer leaders are encouraged to self-design and conduct one more oral health-related activity that they are interested. Necessary support will be provided by the team. We will record details of this peer leader-initiated activity.
- 5) In the 5th or 6th month of intervention, peer leaders will deliver a special talk regarding illness representations for students with existing oral diseases only. The talk will focus on improving illness representation in both cognitive and emotional aspects, and coping strategies will be practiced.

The exact timeslots to conduct the above activities will be decided during discussion with the peer leaders themselves to ensure feasibility and the minimum interruption on their study. However, activities are highly encouraged to be conducted at a monthly frequency.

As a friendly reminder, all S2 students in the intervention group will get a text message from their teachers about the activity details (e.g., place, main theme) from the school one day before each activity will be conducted. Participants will get a stamp from the peer leader after completing each activity. We will use this stamp record to reflect the actual number of intervention activities that the participants are successfully involved.

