## d. Conditions in the control group

Participants in the control group will continue their present practice, and no additional interventions will be given except for pamphlete delivery. We will keep a record of their present practice in detail. Because control groups and intervention groups are in different schools, so the chance for them to get access to the peer-led activities conducted in the intervention group is very low. Contamination would be quite minimum.

## The first follow-up at months 6

The first follow-up at months 6 will include two parts. The first part is to collect participants' selfreported data through survey. An experienced fieldworker who are blind to group allocation will facilitate the survey process. The data collected at month 6 indicates an immediate impact of the intervention, as all the intervention activities will be conducted within this 6-month intervention period. The proposed time interval (6 months) is reasonable and feasible, as 6 months is the most frequently adopted time point to evaluate behaviour changes and the dental visit for checkup is recommended to adolescents every 6 months. We will compare changes before and after this intervention within intervention groups, and we will also investigate the differences between intervention group and control group.

The second part is to collect data to evaluate the intervention implementation process, following the WHO recommendation [39]. We will check participant's exposure to intervention activities. Three indicators will be used, including the percentage of peer leaders who successfully deliver the required number of intervention activities during the intervention period, the coverage rate of

each intervention activity (number of participants in a specific activity divided by number of all S2 adolesents), and the number of intervention activities that each student is actually exposed to. We will collect participant's self-reported data and also check their stamp records for confirmation.

In addition, participant's subjective measures (e.g., rating on whether it's interesting, helpful, informative, comprehensible) towards the intervention activities will be also collected. An evaluation form will be distributed to participants who have participated in at least one of the five intervention activities to collect their opinions on each of these activities.

## The second follow-up at months 12

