The second follow-up at months 12 will include two parts. The first part is to collect participants' self-reported data through survey, the same procedure as the first follow-up at 6 months. The 12-month follow up data suggest a prolonged impact of the intervention, as no intervention activities will be conducted between months 6 and months 12.

The second part is to do dental re-examination, using the same methods and criteria as the baseline examination. We will compare the changes of the oral health status before and after the intervention. The consistency between self-reported healthy oral health behaviors and dental examination outcomes will also be calculated. No dental examination will be conducted at 6-month follow up, as oral health status is not likely to change much within a short time period like 6 months.

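### The recorded health talk goes online with no stated audience or end date, so separate schools do not by themselves support minimal contamination for that component, and viewing may continue unmeasured in months 6 to 12

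*Protocol*

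**What the plan says.** Under Protocol section b, Contents of the intervention activities, five peer-led activities are listed over a 6-month period. The second is a talk guided by the two behavioural theories and including peer leaders' testimonials: "In the 2nd month of intervention, peer leaders will give a specific health talk aiming to raise the awareness of healthy oral behaviors". The item adds: "We will video-record this health talk and make it available online to reach more students". No audience, log-in, posting date or closing date is given there or anywhere else in the protocol.

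Three other places bear on this:

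- **Contamination.** Section d, Conditions in the control group, says of controls that "no additional interventions will be given except for pamphlete delivery". It argues that the arms are in different schools, "so the chance for them to get access to the peer-led activities conducted in the intervention group is very low", and concludes: "Contamination would be quite minimum".
- **Month 12.** The paragraph on the second follow-up takes the 12-month data to suggest a prolonged impact, "as no intervention activities will be conducted between months 6 and months 12".
- **Exposure.** Section b says "Participants will get a stamp from the peer leader after completing each activity". The month-6 follow-up adds self-report, with the stamps used to confirm it. Data processing and analysis then regresses efficacy on the number of activities received and compares subgroups by which activities they received.

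**The concern.** The online recording is not considered in any of the three places that depend on where and when the intervention is received.

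- If control students can view it, the comparison is no longer purely intervention against present practice plus pamphlets, and the difference shrinks toward zero.
- If intervention students can view it after month 6, a difference at month 12 mixes persistence with continued receipt of one component.
- If viewing is not recorded, neither effect can be sized afterwards. The coverage rate, the activity count and the exposure analyses built on them may also misclassify students who saw the talk only on screen.

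**Working it through.** The protocol gives no contamination rate, so there is no figure of its own to reproduce. The main check compares passages; the arithmetic only gives scale.

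**Comparison of passages**

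1. *Premise for low contamination:* separate schools. This covers what happens on school premises: the printed materials and quiz, the live talk, the workshop, the peer-designed activity and the talk for students with oral disease. It does not cover a recording that can be viewed elsewhere. The argument is therefore incomplete for one component of five and intact for the on-site ones.
2. *Premise for month 12:* no activities are conducted after month 6. A recording left online does not contradict that literally. It does allow the month-2 talk to be received in months 6 to 12, which the paragraph does not consider.
3. *Exposure record:* the stamp comes from a peer leader. Self-report is a second source and could include viewing, but no viewing item is described. For controls, the protocol promises a detailed record of present practice, which is not a question about the recording.

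**Scale of possible dilution**

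Inputs from Sample size calculation:

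- Brushing prevalence is 80%. A rise of 20% of that level, read as relative, gives 0.80 × 1.20 = 96%, a difference of 16 points.
- There are 6 schools of 65 students per arm, so 6 × 65 = 390.
- The intra-cluster correlation is 0.05.
- The test is two-sided at 0.05 (from Data processing and analysis).

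Assumption: a fraction c of control students see the recording and each gains the full 16 points. The document gives no value for c.

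- Control prevalence = 80 + 16c, so the remaining contrast = 96 − (80 + 16c) = 16 × (1 − c) points.
- Design effect = 1 + (65 − 1) × 0.05 = 4.2, so the effective size per arm = 390 / 4.2 ≈ 92.9.
- The power column is the normal approximation for two proportions at that effective size.
- The last column assumes 85% of students are retained: 390 × 0.85 = 331.5 per arm, or 55.25 per school, with design effect 1 + 54.25 × 0.05 ≈ 3.71.

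| c | Remaining contrast (points) | Power, 390 per arm | Power, 85% retained |
|---|---|---|---|
| 0% | 16.0 | 92.5% | 91.5% |
| 5% | 15.2 | 90.5% | 89.4% |
| 10% | 14.4 | 88.2% | 86.9% |
| 20% | 12.8 | 82.1% | 80.5% |
| 30% | 11.2 | 74.0% | 72.3% |

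For a given c, the loss of 16c points is an upper bound, because one video is unlikely to carry the whole effect of five activities. The power figures are somewhat optimistic with only six clusters per arm.

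**The case against.** The strongest reply is that open access is inferred from silence. The activities are described as taking place in intervention schools, and the sentence before the one on the recording has teachers encouraging students to attend. In that setting, reaching more students may simply mean students of those schools who missed the talk. Activity reminders go only to S2 students in the intervention group, and nothing describes promoting the recording to control schools. The protocol also claims a low chance of access, not zero. Dilution would not create a false positive, and power stays above 80% at c = 20% even on the upper-bound assumption.

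Most of this stands, and it limits the point. A reader might infer that control students can watch from month 2, that the contamination argument collapses, or that month 12 measures ongoing exposure and not persistence. The document supports none of these:

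- Only the talk is dated to month 2; the posting is not.
- School separation still protects the on-site activities.
- Months 6 to 12 are described as having no activities conducted, not as free of all exposure. Any distortion depends on how many students actually watch.
- Prolonged impact is an interpretation of the month-12 data, not one of the listed objectives.

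The reply does not remove the rest. Even if the recording is meant only for intervention schools, nothing restricts it to them, they could still view it after month 6, and no way of recording their viewing is described.

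**Conclusion.** The point holds in limited form. Separate schools do not by themselves support the minimal-contamination statement for the online talk. Possible viewing after month 6 weakens the prolonged-impact reading without overturning it. Online viewing may be miscounted in the exposure analyses.

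The direction of any contamination bias is toward no effect. Its size is unknown, since it depends on the unstated audience and the unknown viewing fraction. On the full-effect assumption and the 80% to 96% reading, 5% to 30% viewing among controls would cost at most 0.8 to 4.8 of the 16 points (16 × 0.05 and 16 × 0.30). Modest viewing would not undermine the trial. The change is worth making because it costs little and, as written, neither control viewing nor late viewing could be estimated afterwards.

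**What to change.** - **Section b, Contents of the intervention activities:** state that the recording is released only through a restricted link to S2 students in intervention schools, closes at the end of the 6-month intervention period, and opens publicly, including to control schools, only after month-12 data collection.
- **Month-6 and month-12 surveys, both arms:** add one item asking whether the student has seen the talk, so that viewing can enter the exposure measures and any control viewing can be reported.
- **Section d, Conditions in the control group:** amend the contamination paragraph to address the recording as well as the separation of schools.

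The cost is a link setting, two dates, one survey item and a few sentences of text. The downside is that public reach is delayed until after month 12.

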### c. Intervention materials development

All the materials needed in the activities will be designed by an expert panel, including a behavioral scientist, a health psychologist, an epidemiologist, and a registed specialist in Pediatric Dentistry. The development of such materials will be mainly guided by SCT and HBM [18, 31]. Our team is experienced in materials development, and our previous work has been well acknowledged and disseminated in multiple settings, such as clinics, kindergartens, and primary schools.

## d. Conditions in the control group

Participants in the control group will continue their present practice, and no additional interventions will be given except for pamphlete delivery. We will keep a record of their present practice in detail. Because control groups and intervention groups are in different schools, so the chance for them to get access to the peer-led activities conducted in the intervention group is very low. Contamination would be quite minimum.

## The first follow-up at months 6

The first follow-up at months 6 will include two parts. The first part is to collect participants' selfreported data through survey. An experienced fieldworker who are blind to group allocation will facilitate the survey process. The data collected at month 6 indicates an immediate impact of the intervention, as all the intervention activities will be conducted within this 6-month intervention period. The proposed time interval (6 months) is reasonable and feasible, as 6 months is the most frequently adopted time point to evaluate behaviour changes and the dental visit for checkup is recommended to adolescents every 6 months. We will compare changes before and after this intervention within intervention groups, and we will also investigate the differences between intervention group and control group.

The second part is to collect data to evaluate the intervention implementation process, following the WHO recommendation [39]. We will check participant's exposure to intervention activities. Three indicators will be used, including the percentage of peer leaders who successfully deliver the required number of intervention activities during the intervention period, the coverage rate of

each intervention activity (number of participants in a specific activity divided by number of all S2 adolesents), and the number of intervention activities that each student is actually exposed to. We will collect participant's self-reported data and also check their stamp records for confirmation.

In addition, participant's subjective measures (e.g., rating on whether it's interesting, helpful, informative, comprehensible) towards the intervention activities will be also collected. An evaluation form will be distributed to participants who have participated in at least one of the five intervention activities to collect their opinions on each of these activities.

## The second follow-up at months 12

The second follow-up at months 12 will include two parts. The first part is to collect participants' self-reported data through survey, the same procedure as the first follow-up at 6 months. The 12-month follow up data suggest a prolonged impact of the intervention, as no intervention activities will be conducted between months 6 and months 12.

The second part is to do dental re-examination, using the same methods and criteria as the baseline examination. We will compare the changes of the oral health status before and after the intervention. The consistency between self-reported healthy oral health behaviors and dental examination outcomes will also be calculated. No dental examination will be conducted at 6-month follow up, as oral health status is not likely to change much within a short time period like 6 months.

## Outcome indicators and potential confounders

The primary outcome is the prevalence of performing each of the three types of healthy oral health behaviors, including tooth brushing, dental flossing, and dental visit. The increase in performing healthy oral behaviors is the key of public health significance. The secondary outcome is the prevalence and severity of oral diseases, including dental caries and poor periodontal status. The third outcome is the prevalence of theory-based constructs regarding the above healthy oral behaviors, including perceived benefits, perceived barriers, perceived severity, self-efficacy and behavioural capability.

Potential confounders include socio-demographic characteristics, pre-existing oral diseases, and utilization of dental services (except for dental check-up) during the follow-up period. Such information will be collected at the baseline and follow-up survey, and between-group differences will be tested for statistical significance. Any significant differences will be adjusted in the analysis evaluating the efficacy of the intervention as compared to the control group.

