## (iv) Data processing and analysis

The intra- and inter-examiner reliabilities of assessing PI, DMFT and CPI at the tooth level will be tested through the use of the kappa statistic. Data of DMFT and CPI at the tooth level will be used to generate the oral health status at the subject level.

Intention-to-treat analysis will be conducted. Multiple imputation methods will be used [40] to deal with missing data if it occurs. Between-group (intervention versus control) baseline differences in the frequency distributions of potential confounders will be compared by using chi-square test, t-test, Mann-Whitney test or other statistics. The absolute and relative risks and number needed to treat (and 95% confidence intervals) for the binary outcomes comparing the two groups at months 6 and 12 will be derived. Comparisons between the intervention and control groups will be made for all binary outcomes, adjusting for any potential confounders showing p<.10 in the between-group baseline comparisons (if any), using modified Poisson regression with robust sandwich variance estimation. SPSS will be used for data analysis; p<.05 (2-sided) will be taken as statistically significant. The research team is very experienced in performing data analysis.

Based on the number of intervention activities that the participants are actually exposed to, we will conduct a regression analysis to explore whether the incease of numbers of activities will increase the efficacy of the intervention. Subgroup analysis will also be conducted to compare the efficacy among participants who are exposed to different (or different combinations of) intervention activities.

We will consider the variables of oral health status at baseline, and test its mediating effect on the relationship between theory-based cognitions (and changes) and healthy oral behaviors (and changes). In statistics, a mediating effect can be tested by using an interaction term, whereby the effect of an independent variable on a dependent variable varies by the level of the mediator [41]. The mediating hypothesis is supported if the regression coefficient of the interaction term onto the dependent variable is statistically significant.

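### Two covariate-adjustment rules conflict, and one can adjust the intention-to-treat comparison for dental-service use that arises after allocation

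*Protocol*

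**What the plan says.** Two sections of the Protocol state how covariates enter the efficacy comparison.

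- **Outcome indicators and potential confounders.** Besides background characteristics and existing oral disease, the potential confounders include "utilization of dental services (except for dental check-up) during the follow-up period". On timing and testing: "Such information will be collected at the baseline and follow-up survey, and between-group differences will be tested for statistical significance". On use: "Any significant differences will be adjusted in the analysis evaluating the efficacy of the intervention as compared to the control group". No threshold is given.
- **(iv) Data processing and analysis.** "Intention-to-treat analysis will be conducted". Baseline differences "will be compared by using chi-square test, t-test, Mann-Whitney test or other statistics". Then: "Comparisons between the intervention and control groups will be made for all binary outcomes", by modified Poisson regression, "adjusting for any potential confounders showing p<.10 in the between-group baseline comparisons (if any"). The general level is "p<.05 (2-sided) will be taken as statistically significant".

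Neither section refers to the other, and neither rule is labelled primary or sensitivity.

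**The concern.** There are two faults.

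**The rules cannot both govern.** A variable that describes the follow-up period does not exist at baseline. It can enter the model under the first rule and never under the second.

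**The first rule admits a post-allocation covariate.** The primary aim includes raising dental check-up visits, and the third-month workshop practises skills for dental visits. A prompted check-up can lead to a filling or other treatment, which is the kind of service use the confounder list counts. Chance aside, the rule is triggered when the intervention has shifted service use, which is when adjusting for it can distort the total effect that an intention-to-treat analysis estimates. The exposed results are the dental-visit outcome, one of the three primary behaviours, and the clinical outcomes, since filled teeth count in DMFT.

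Both rules also choose covariates by between-arm significance tests, so the model depends on the realised data.

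**Working it through.** **1. The rules side by side**

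| | Outcome indicators section | Data processing section |
|---|---|---|
| Differences that count | baseline and follow-up | baseline only |
| Threshold | significant (no figure; general level p<.05) | p<.10 |
| Outcomes covered | efficacy analysis, unrestricted | binary outcomes |
| Follow-up service use | can enter | cannot enter |

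The timing conflict needs no inference. The threshold conflict depends on reading *significant* as p<.05. On scope, the Hypotheses section speaks of construct scores and DMFT is a count. For outcomes analysed in that form, the first rule is the only one stated.

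**2. Effect on the dental-visit comparison**

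The Protocol gives no rates, so every input in this step is assumed: check-up attendance 33% (control) v 50% (intervention), treatment in a fraction *t* of attenders and 5% of non-attenders.

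Crude RR = 0.50/0.33 = 1.515.

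Service use = P(check-up) × *t* + P(no check-up) × 0.05. For *t* = 0.6:
- control: 0.33×0.6 + 0.67×0.05 = 23.2%
- intervention: 0.50×0.6 + 0.50×0.05 = 32.5%

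A Poisson model with arm and service use, fitted to the exact cell probabilities, gives:

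| *t* | Service use, control v intervention | Adjusted RR |
|---|---|---|
| 0.20 | 10.0% v 12.5% | 1.483 |
| 0.40 | 16.6% v 22.5% | 1.406 |
| 0.60 | 23.2% v 32.5% | 1.309 |

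Hand check for *t* = 0.6 by Mantel-Haenszel. Per-arm probabilities of check-up among the treated are 0.300 (intervention) and 0.198 (control); among the untreated, 0.200 and 0.132.
- Numerator: 0.300×0.2315/0.5565 + 0.200×0.7685/1.4435 = 0.2313
- Denominator: 0.198×0.325/0.5565 + 0.132×0.675/1.4435 = 0.1774
- Ratio: 1.304, close to the model's 1.309

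Sensitivity:
- Control attendance 20% or 50% at the same crude RR: adjusted RR 1.30–1.49.
- Non-attenders treated 10% instead of 5%: 1.50/1.44/1.35. At 20%: 1.515/1.49/1.42.
- Treatment equally common in attenders and non-attenders (40%): 1.515, unchanged.

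**3. How often the rule would select service use (p<.05)**

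Cluster size *m* = 65 is from Sample size calculation; *m* = 55 assumes about 15% loss. Six schools per arm give 330 students at *m* = 55. The probability is Φ((Δ − 1.96·SE₀)/SE₁) plus the opposite tail, where SE₀ is the ordinary pooled standard error and SE₁ the true one, with variance multiplied by DE = 1 + (m − 1)·ICC.

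- Independent students, 330 per arm: 18%, 49% and 77% for *t* = 0.2, 0.4 and 0.6.
- ICC 0.05, *m* = 55–65: 38–69%, against 31–34% if the intervention has not shifted service use.
- ICC 0.01: 24–77%, against 11–13%.

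**4. Tooth brushing**

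Assume 80% v 88% (RR 1.10), with service users brushing 0.8 to 1.1 times as often as non-users. Adjusted RR is 1.114 to 1.094 with service use 16.6% v 22.5%, and 1.122 to 1.090 with 23.2% v 32.5%. The shift is small and can go either way.

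**5. The significance gate**

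For a covariate with no systematic difference, tested as if students were independent, the flag rate is 2·(1 − Φ(z/√DE)).

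| ICC | m | DE | p<.05 | p<.10 |
|---|---|---|---|---|
| 0.05 | 55 | 3.70 | 31% | 39% |
| 0.05 | 65 | 4.20 | 34% | 42% |
| 0.01 | 55 | 1.54 | 11% | 19% |
| 0.01 | 65 | 1.64 | 13% | 20% |

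The Protocol sets ICC 0.05 for its sample size; applying it to covariates is an assumption.

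**The case against.** **The analysis section governs.** It names tests, a model and a threshold, while the other section does not. On a specific-over-general reading, follow-up service use never enters the models for binary outcomes, including all three primary behaviours. That is a sensible way to resolve the conflict, but the Protocol does not adopt it, and the other section speaks directly of the analysis that evaluates efficacy.

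**Check-ups are excluded from the covariate.** This keeps the outcome itself out of the model. It does not keep out treatment that follows a prompted check-up.

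**The mechanism is not a separate pathway.** In step 2 treatment follows attendance, so the covariate is downstream of the outcome itself. That is correct, but it is no better a reason to adjust. Treatment that changes DMFT is the clearer pathway, though it bears on a secondary outcome.

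**The size is assumed.** It is. The low end depends on few non-attenders being treated, and every adjusted ratio stays well above 1.

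**Choosing covariates by test is a matter of preference.** Partly so. No effect on type I error or power is shown, and the Protocol's wording leaves room for cluster-aware tests.

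**Non-binary models belong in an analysis plan, and the outcomes section calls the third outcome a prevalence.** Both are fair, so the scope point is secondary.

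**Conclusion.** The concern holds. The Protocol states two adjustment rules that differ in timing, probably in threshold, and in scope. One of them can condition the intention-to-treat comparison on a variable that arises after allocation. This is a stated rule that needs correcting, not missing detail.

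Bias is a risk, not a certainty: the intervention must shift service use, and service use must be related to the outcome. Under the assumptions shown, a dental-visit risk ratio of 1.52 could be reported anywhere from unchanged down to about 1.30. The effect on tooth brushing, which the Protocol treats as its leading primary indicator, is negligible to small. The significance gate is a lesser fault that makes the covariate set unstable from one realisation of the trial to another. The correction should be made, but it does not threaten the trial's design.

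**What to change.** 1. Replace the two statements with a single adjustment rule, given in one section and cross-referenced in the other, that covers all outcomes, binary or not.
2. Take follow-up dental-service use out of the adjustment set for the efficacy comparison. Report it by arm, descriptively or as a process outcome. If an adjusted analysis is still wanted, label it as supportive and say that it does not estimate the intention-to-treat effect.
3. Replace selection by significance test with a covariate set named in advance and limited to baseline variables. As an optional improvement, include the baseline value of each outcome; the baseline survey and dental examination already collect these.

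The cost is wording only. No new data, visits or participants are needed.
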